Before and after the acute resistance exercise protocols (PRE, IP, 60min), participants will complete a questionnaire to assess GI symptoms adapted from a previous study (4). The questionnaire is organized into three sections, each including four to seven questions. Section 1 addresses upper abdominal issues (reflux, heartburn, bloating, cramps, vomiting, nausea); Section 2, lower abdominal issues (intestinal cramps, flatulence, urge to defecate, left abdominal pain, right abdominal pain, loose stool, diarrhea); and Section 3, systemic issues (dizziness, headache, muscle cramp, urge to urinate). Each participant will complete the 17 items on a 10-point scale ranging from 0, no problem at all, to 9, the worst it has ever been.

Blood Collection, Handling and Storage

Blood samples during the experimental trials (PRE, IP, 15min, 30min, 60min) will be drawn from a 20g Teflon™ cannula placed in an antecubital vein, which will remain patent via an isotonic saline flush. Blood samples will be obtained from the cannula with a plastic syringe prior to exercise (PRE), immediately-post (IP), 15-, 30-, and 60min post-exercise. Blood samples will be deposited into untreated (for serum collection), as well as EDTA- and heparin-treated (for plasma collection) BD Vacutainer® tubes. Untreated tubes will clot for 30 minutes prior to centrifugation, while treated tubes will be centrifuged immediately for 15 min at 1500 x g at 4°C. The resulting serum and plasma will be aliquoted and stored at -80°C until analysis. Samples will be thawed only once for biochemical analysis.

Assessment of intestinal damage, permeability, and inflammation

I-FABP concentrations from EDTA plasma will be measured using an ELISA (RayBioTech Inc., Norcross, GA) according to the manufacturer's instructions. Lactulose/Rhamnose (LR) ratio will be assessed using a previously published protocol (2), with the modification of using L-rhamnose instead of mannitol as the monosaccharide probe (5, 6). Briefly, at baseline, participants will drink a standardized sugar solution containing 5 g lactulose, 2 g rhamnose, 1 g sucrose, and 0.5 g D-xylose in a total of 50

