mL water. Saccharide concentrations will then be determined from serum samples at all time-points and the LR ratio will be calculated. Serum will be analyzed for endotoxin concentration using a commercially available kinetic limulus amebocyte lysate (LAL) assay (Lonza; Allendale, NJ). Circulating plasma concentrations of the pro-inflammatory cytokine TNF- α will be assayed via commercially available ELSIA kits (ALPCO, Salem, NH, USA).

For fecal analysis, feces will be thawed, and 100 mg will be added to 4.9 ml of extraction buffer (0.1 M Tris, 0.15 M NaCl, 1.0 M urea, 10 mM CaCl₂ 2H₂O, 0.1 M citric acid, 0.5% BSA, pH 8.0). After 30 minutes shaking, 1 ml of suspension will be centrifuged at 10,000 rpm for 20 minutes at 4°C. Fecal supernatants will be assayed for calprotectin via ELISA (Eagle Biosciences, Nashua, NH) using manufacturer's instructions. A summary of the markers of interest is presented in Table 1.

Table 1. Biochemical Markers of Interest

Marker	~24H Pre	Pre	IP	15min	30min	60min	~24H Post
Blood							
I-FABP	X	X	X	X	X	X	
Endotoxin (LAL)	X	X	X	X	X	X	
Lactulose/Rhamnose Ratio	X	X	X	X	X	X	
Fecal							
Shallow Shotgun Metagenomics	X						
SCFA	X						

I-FABP = Intestinal Fatty-acid Binding Protein, LAL = limulus amebocyte lysate, SCFA = Short-Chain Fatty Acids. 24H Pre= 24hours before exercise, Pre= Pre-exercise, IP = Immediately post-exercise, 24H = 24-hours post-exercise.

Fecal Shallow Shotgun Metagenomics

After collection, 10-20g feces will be separated into sterile collection containers and immediately frozen at -20°C. After thawing, DNA will be extracted from samples using the Qiagen MagAttract PowerSoil DNA KF Kit (formerly MO BIO PowerSoil DNA Kit) optimized for the ThermoFisher KingFisher robot according to manufacturer's instructions. Whole DNA will be prepared for sequencing using the Illumina Nextera Flex DNA library prep kit. Samples will be barcoded and mixed together for sequencing. The mix will then be subjected to paired-end sequencing using Illumina sequencers. Paired reads will be concatenated and processed to remove adaptors, barcodes and low-quality reads as well as contaminant sequences (typically host DNA). Sequences will then be mapped to databases to obtain taxonomic and functional profiles. Sequencing will be performed on the Illumina NextSeq. The number of reads targeted ranges from 0.5 to 3 million.

Fecal Short-Chain Fatty Acid Analysis

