Prior to analysis all data will be assessed to ensure normal distribution, homogeneity of variance and sphericity. Non-normally distributed data will be transformed using the natural log (LN) and if sphericity is violated, a Greenhouse Geisser correction will be applied. General Linear Model (GLM) repeated measures analyses [time x trial x sex] will be used to compare trials (RE, CON) for all variables. Following a significant F ratio, separate one-way repeated-measures ANOVA will be performed to assess the effect of time during each trial, and separate paired-samples t-tests will be used to compare trials at each time point. Separate independent t-tests will also be used to evaluate specific differences between sexes when applicable. An alpha level of $p < 0.05$ will be considered statistically significant for all comparisons. Based on a standard deviation of $511 \text{ pg}\cdot\text{ml}^{-1}$ and $347 \text{ pg}\cdot\text{ml}^{-1}$ for post-exertional I-FABP for males and females, respectively (8) and using a standard alpha (0.05) and beta value (0.8), a sample size of $n= 4$ per group was calculated to have adequate statistical precision to detect a $> 110\%$ increase in I-FABP post-exercise. Such increases in I-FABP after exercise have also been correlated with the magnitude of intestinal permeability (9). Current participant numbers are also in accordance with sufficient statistical precision to detect significant differences in gastrointestinal symptoms (1). From the metagenome sequencing the group comparisons of gut microbiota will be analyzed with non-parametric Wilcoxon matched-pair signed rank test and corrected for multiple comparison with Benjamini-Hochberg procedure. Regarding the taxonomic data, all analyses will be made with Quantitative Insights Into Microbial Ecology (QIIME) open-sourced software from the randomly subsampled Operational Taxonomic Unit (OTU) table with rarefaction level matching the sample with the lowest total OTU count. The bacterial diversity of the samples (α -diversity metrics) and statistically significant differences in the OTU abundances will be computed with QIIME. Any correlations between non-normally distributed gut microbiota and other variables will be determined using Spearman's rank correlation coefficient in SPSS. The GLM in SPSS will be used to determine whether differences in taxa occur due to biological sex or whether they are dependent on age, weight, body fat %, total energy intake, macronutrient composition, or fiber.

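### No primary outcome or model effect is named, so if any of four or five outcomes may carry the exercise claim at p < 0.05, the chance of a false claim is about 10–24% rather than 5%

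*Protocol*

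**What the plan says.** All of the inferential rules are in the protocol's Statistical Analysis section.

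- **Model and scope.** "General Linear Model (GLM) repeated measures analyses [time x trial x sex] will be used to compare trials (RE, CON) for all variables". No variable is singled out.
- **Follow-up.** "Following a significant F ratio, separate one-way repeated-measures ANOVA will be performed to assess the effect of time during each trial". The two trials are then set against each other by paired t-tests, one per sampling time. Which F ratio has to be significant is not stated.
- **Threshold.** A p-value below 0.05 "will be considered statistically significant for all comparisons".
- **Multiplicity.** The only control is for the gut microbiota comparisons, which are "corrected for multiple comparison with Benjamini-Hochberg procedure".
- **Sample size.** The calculation (n = 4 per group, SD 511 and 347 pg/ml, more than a 110% rise) is for I-FABP. A later sentence says, without figures, that the numbers also suffice for GI symptoms.

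The outcomes measured repeatedly in both trials are set out in two other sections. The section on intestinal damage, permeability and inflammation covers I-FABP, lactulose/rhamnose ratio, endotoxin and TNF-alpha. It closes with "A summary of the markers of interest is presented in Table 1"; that table lists the first three blood markers without ranking them and omits TNF-alpha. The section on acute GI distress questionnaires adds a 17-item symptom score in three parts at PRE, IP and 60 min.

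**The concern.** The outcomes measure different things: enterocyte damage, permeability, endotoxaemia, inflammation and symptoms. They can disagree. The protocol does not say which of them answers the question of whether resistance exercise affects the gut, or which F test within the model answers it. A null I-FABP result could therefore be set aside in favour of a significant result on another marker, and nothing in the text would stand against that. If the conclusion may rest on whichever outcome turns out significant, 0.05 is not the error rate of that conclusion.

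This is more than detail held over for a statistical analysis plan. The protocol itself fixes a flat rule (all variables, an unspecified F ratio, 0.05 throughout), and a later plan that ranked the outcomes would have to depart from it. Adjusting only the t-tests across time points would not help, because the choice among outcomes is made earlier, at the F-test stage.

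**Working it through.** **Inputs from the protocol.** Alpha is 0.05 per comparison. There are 12–15 men and 12–15 women in a two-trial cross-over. Blood is drawn at five times and symptoms are scored at three. Five outcomes enter the trial comparison, or four if only the blood markers are counted or if TNF-alpha is left out because it is not in Table 1. Stool is collected only before the second visit, so the fecal measures do not enter.

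**Inputs assumed.** Between-outcome correlation ρ is not given and is taken from 0 to 0.9. No outcome has a trial or trial-by-sex effect, and sphericity holds.

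**The plan's own figure.** The n = 4 per group cannot be reproduced, because the I-FABP baseline mean is missing. For a two-sided two-group comparison, the detectable difference at n = 4 is SD × (1.960 + 0.842) × √(2/4). This is 1,012 pg/ml for men and 687 pg/ml for women. A 110% rise of that size implies baselines of 1,012/1.1 = 920 and 687/1.1 = 625 pg/ml. For the present point, what matters is only that I-FABP is the one outcome with a calculation at all.

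**Step 1: independent outcomes, one time × trial F test each.** P(at least one false positive) = 1 − 0.95^k.
- k = 4: 1 − 0.8145 = 18.5%.
- k = 5: 1 − 0.7738 = 22.6%.

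**Step 2: correlated outcomes.** Three calculations were run: equicorrelated two-sided z tests (400,000 draws), and two simulations of the repeated-measures F tests. Simulation A had 4,000 runs per setting, 12 or 15 per sex, three times for symptoms, and a subject-by-trial SD of 0.8 of the residual SD. Simulation B had 6,000 runs per setting, N = 24 or 30, and five times for every outcome.

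| Outcomes, method | ρ = 0 | 0.5 | 0.7 | 0.8 | 0.9 |
|---|---|---|---|---|---|
| 4, z tests | 18.5% | 15.6% | 13.1% | 11.3% | 9.4% |
| 4, F tests (A) | 20% | 15.1–16.3% | – | 12% | – |
| 5, z tests | 22.8% | 18.4% | 14.7% | 12.7% | 10.2% |
| 5, F tests (A) | 24% | 18.5–19.5% | – | 15% | – |
| 5, F tests (B) | 21.6–23.1% | 18.7–19.8% | 15.8–16.1% | – | – |

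Single-test rates in simulation A were 0.042–0.058, so the excess comes from the number of tests. The 24% at ρ = 0 is simulated. The exact value is 22.6%, with a Monte Carlo standard error of √(0.226 × 0.774/4,000) = 0.7 percentage points, so the gap is about two standard errors. The figures at ρ = 0.9 rest on the z approximation, which runs slightly below the F-test simulations where both are available. Overall the rate is about 10–24%, and about 15–20% at ρ = 0.5.

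**Step 3: if the trial main effect may also count.** Over five outcomes, simulation B gives 40% at ρ = 0, 34–35% at 0.5 and 29% at 0.7. Over the four blood markers at 0.5, simulation A gives 29%. For a single outcome the rate is about 10%, so naming I-FABP without naming the effect would not restore 5%.

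**Step 4: if some outcomes truly change.** Only the remaining nulls can produce a false positive. With one of the five truly affected, four remain: 18.5% at ρ = 0 and 15.6% at 0.5 (z tests). With two affected, three remain: 1 − 0.95³ = 14.3%, and 12.6% at 0.5.

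**Step 5: after naming one outcome and one effect.** The rate is 5% (simulated 4.8% for time × trial).

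**The case against.** The best reply is that I-FABP is the implied main outcome. It alone has an SD, an effect size and a calculated n, and the exercise protocol is justified by a similar one that raised I-FABP. The follow-up tests (time within trial, trials at each time) are also the usual breakdown of a time × trial interaction. This has force: a reader might infer from the flat 0.05 rule that every outcome has equal standing, and the sample-size text does not support that. But the protocol never turns the lead into a designation, cites GI symptoms as a second justification, and leaves the significant F ratio unspecified.

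A second reply is that, in a mechanistic study, each marker can be its own question at 5%. That is a fair convention where each result is reported as such. The family-wise rate applies only if any one outcome may carry a common exercise claim. The protocol does not state such a claim, but neither does it rule one out.

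A reader might also count all four trial-related F tests over five outcomes, which gives about 56–57% at ρ = 0.5. That total should not be used here. Trial × sex and time × trial × sex address whether the sexes differ, not whether exercise affects the gut.

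**Conclusion.** The point holds in a limited form. The protocol fixes one model and one threshold for all variables and does not name the outcome or effect that decides the trial. If any of the four or five outcomes may carry the exercise claim through its time × trial test, the chance of at least one false positive is roughly two to nearly five times the stated 5%. This is conditional on no outcome having a trial effect and on a between-outcome correlation that the protocol does not give. Fifteen per cent is therefore not a floor: with one test per outcome, the rate falls below that at high correlations, and it also falls if I-FABP truly rises, as the protocol expects. It should be corrected before data are seen, but it does not invalidate the design.

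**What to change.** In Statistical Analysis, state that:

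1. The primary test is the time × trial (RE versus CON) interaction for plasma I-FABP at two-sided 0.05.
2. Endotoxin, lactulose/rhamnose ratio, TNF-alpha and one GI symptom total are secondary. They are either Holm-adjusted across their four time × trial tests (smallest p-value against 0.05/4 = 0.0125) or reported as exploratory.
3. The time × trial × sex test for I-FABP is a separately labelled secondary question. It need not be gated on the primary result: the protocol recruits equal numbers of men and women and puts sex in the model, so nothing in it makes the sex question subordinate.
4. All remaining F tests are exploratory, and the sentence applying 0.05 to every comparison is reworded to match.

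This costs a few sentences and no extra participants, visits or assays. The downside is that a positive result on another marker becomes supportive rather than decisive, and Holm-adjusted secondaries lose some power.

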Experimental Approach to the Problem

Research Design

Twenty-four to Thirty healthy, resistance-trained men (n=12-15) and women (n=12-15) between the ages of 18 and 35 will be recruited for this randomized, cross-over investigation. In order to be considered resistance trained, participants will need to have been engaged in resistance trained for ≥ 1 year prior to study enrollment and must be able to leg press at least 2x their bodyweight. Participants must also be free of any physical limitations, metabolic or cardiovascular disorders, and musculoskeletal injuries. Females will be excluded if they are not eumenorrheic and/or report the use of hormone-based contraceptives (e.g. oral contraceptive pill) within the previous 3 months. For female participants, all experimental sessions will take place within the same phase of their menstrual cycle. Furthermore, all participants will be asked not take any other nutritional supplements, performance enhancing drugs, and non-steroidal anti-inflammatory drugs (NSAIDs) throughout the duration of their enrolment in the study. Additionally, participants will be excluded if they have a history of antibiotics or intentionally consumed probiotics in the two months prior to enrollment in the study. If a participant has recently consumed probiotics, an 8-week washout period will be required before the participant is enrolled in the study. The study protocol will be approved by the Lipscomb University Institutional Review Board before participant enrollment.

Testing Procedures

Informed Consent & Questionnaires

Following an explanation of all study protocols, benefits, and risks, each participant will provide their written informed consent prior to participation in this study. Furthermore, participants will complete a PARQ2018+, health and activity questionnaire, food frequency questionnaire, and the Gastrointestinal Symptom Rating Scale (GSRS). The GSRS is an instrument of 15 items combined into five symptom groups representing Reflux, Abdominal pain, Indigestion, Diarrhea and Constipation. The GSRS has a seven-point graded Likert-type scale where 1 signifies absence of troublesome symptoms and 7 represents very troublesome symptoms. The reliability and validity of the GSRS has been previously established (3). The food frequency questionnaire will be used as an additional assessment tool for account for macronutrient and fiber intake when making gut composition comparisons.

Anthropometric & Body Composition Assessment

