During the initial visit to the lab, participants will establish their 1-repetition maximal strength (1RM) on the leg press and leg extension exercises. Each participant will complete a standardized warm-up before the 1RM strength session involving 5 minutes of cycling on a cycle ergometer against low resistance, 10 body-weight squats, 10 body weight walking lunges, 10 dynamic walking hamstring stretches, and 10 dynamic walking quadriceps stretches. The 1RM tests will be performed using methods previously described for the leg press and leg extension exercises. Two warm-up sets utilizing a resistance of approximately 40-60% and 60-80% of their estimated maximum for the exercise will be performed. For both exercises, 3-4 subsequent, maximal trials will be completed to determine the 1RM. A 3-5 min rest period will be provided between each trial. Trials which do not meet the range of motion standards for each exercise or where correct technique is not used will be discarded. Foot positioning on leg press sled as well as equipment placement (back, knee, and leg positions) for leg extension will be measured, recorded, and replicated for each participant on subsequent visits. Additionally, any notable attire (such as lifting shoes), which may influence a participant's performance, will be recorded and replicated for each subsequent visit.

Visit 2-3

Study Controls

Following baseline measurements, participants will report to the lab on two additional occasions to complete each experimental condition. On the morning of each visit, participants will be asked to report to the Human Performance Lab (HPL) fasted for 12 hours and asked to refrained from all forms of moderate to vigorous leg exercise over the previous 72 hours. They will also be requested to report after obtaining at least 8-h of sleep and not to have consumed alcohol, nicotine, or any other drug for the previous 36 hours while abstaining from caffeine for the previous 12 hours. To promote hydration, participants will be asked to consume ~500ml of water the night before reporting to the lab, and the morning of each exercise treatment.

Dietary Logs

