Experimental trials will be completed in a balanced, randomized order with each trial being separated by a minimum of one week to warrant adequate recovery. An overview of the acute resistance exercise protocols is presented in Figure 1. All experimental trials will also be performed within a 2-hour window to avoid diurnal variations. Ample hydration status will be verified (USG ≤ 1.020 defined as euhydration) via urine samples collected upon arrival to the HPL and analyzed for specific gravity (USG) by refractometry. During the exercise experimental trial, participants will perform the same standardized warm-up routine described earlier for 1RM testing, followed by either a resistance exercise protocol, consisting of the squat, seated shoulder press, deadlift, bent-over row, and leg press exercises. The exercise protocol will utilize a load of 70% 1-RM for 4 sets of 10 repetitions and a 90-second rest period length between sets and exercises. The control session will consist of participants completing assessments but will rest seated for 40 minutes instead of exercising. Treatment order (control or exercise) will be randomized using a random number generator. A similar exercise protocol has been demonstrated to significantly elevate I-FABP, a marker of gut permeability (25). During each protocol, if the participant is unable to complete the desired number of repetitions, spotters will provide assistance until the subject completes the remaining repetitions. Immediately upon completion of the acute resistance exercise bout, participants will complete IP assessments.

[figure not shown]

Figure 1. Acute Resistance Exercise Protocol Overview. PRE = Pre-exercise; IP = Immediately-post exercise. RE = Resistance Exercise; GI = Gastrointestinal; 1RM = 1-Repetition Maximum

Acute GI Distress Questionnaires

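### The crossover analysis has no period or order term, so visit-to-visit change stays in the error and an unequal order would go uncorrected

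*Protocol*

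**What the plan says.** The opening Research Design section describes a crossover: "Twenty-four to Thirty healthy, resistance-trained men (n=12-15) and women (n=12-15) between the ages of 18 and 35 will be recruited for this randomized, cross-over investigation". Under Study Controls (Visit 2-3), "participants will report to the lab on two additional occasions to complete each experimental condition", so there are two periods.

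The Resistance Exercise Protocol section states that "Experimental trials will be completed in a balanced, randomized order with each trial being separated by a minimum of one week to warrant adequate recovery" and that "Treatment order (control or exercise) will be randomized using a random number generator". It describes no block, fixed list or stratification by sex.

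The Statistical Analysis section gives the model: "General Linear Model (GLM) repeated measures analyses [time x trial x sex] will be used to compare trials (RE, CON) for all variables". After a significant F ratio, "separate paired-samples t-tests will be used to compare trials at each time point". For sex, "Separate independent t-tests will also be used to evaluate specific differences between sexes when applicable". Neither the model nor the follow-up tests contain a period, order or sequence factor.

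**The concern.** Order is randomised in a crossover because the two visits may differ for reasons unrelated to the condition, such as a first cannulation, familiarity with the procedures, or a diet that is free the first time and replicated the second. An analysis that ignores order has to put that difference somewhere:

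- If the two orders are equally frequent, it goes into the error term and power is lost.
- If they are not, part of it goes into the estimated difference between trials.
- If the inequality differs between men and women, part of it appears as a sex difference in the response to exercise, which the model is meant to test.

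**Working it through.** **The plan's own figure.** The only calculation in the Statistical Analysis section is n = 4 per group for a rise of more than 110% in I-FABP. It involves no period effect, and it cannot be reproduced because no baseline mean is given. It is not used below.

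**Inputs.** N = 24 (12 per sex, the lower end of the stated range) and two-sided alpha 0.05 (the protocol gives 0.05 without sidedness). The remaining inputs are assumptions: a true RE-CON difference of 0.6 SD, which gives about 80% power at N = 24, and a period effect π (second visit minus first) of 0, 0.25, 0.5 or 1.0. Both are in units of the SD of the within-person difference.

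**Model.** For each person, d = RE minus CON = δ + πs + e, with s = +1 if exercise comes second, s = −1 if it comes first, and SD(e) = 1. The planned paired comparison uses the mean of d and omits s.

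**1. Balanced order, 12:12.** The mean of s is 0, so the bias is 0. The sample variance of d is on average 1 + π² × 24/23:

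- π = 0.25: 1 + 0.0625 × 24/23 = 1.07, SD 1.03
- π = 0.5: 1 + 0.25 × 24/23 = 1.26, SD 1.12
- π = 1.0: 1 + 1 × 24/23 = 2.04, SD 1.43

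The standard error is overstated by that factor. Simulation gives:

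| π (SD) | Power, no period term | Power, with period term | Type I error, no period term |
|---|---|---|---|
| 0 | 0.80 | 0.80 | about 5% |
| 0.25 | 0.79 | 0.80 | 4.4% |
| 0.5 | 0.73 | 0.80 | 2.9% |
| 1.0 | 0.50 | 0.80 | 0.5–0.6% |

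The unadjusted trial x sex test is conservative in the same way (2.9% at π = 0.5).

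**2. Unequal order.** The realised shift in RE-CON is π × (difference between the two order counts)/N. At π = 0.5:

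- 8:7 within a sex of 15: 0.5 × 1/15 = 0.033 SD in that sex
- 10:14 overall: 0.5 × 4/24 = 0.083 SD; type I error about 4%
- 8:16 overall: 0.5 × 8/24 = 0.17 SD; type I error about 8.5%, against about 5% with the term
- men 8:4 and women 4:8: trial x sex shifts by 0.5 × (1/3 + 1/3) = 0.33 SD; type I error about 8%

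**3. How often, if order were drawn separately for each person (an assumption).**

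- Exact balance at 24: C(24,12)/2^24 = 0.16
- Exact balance in both sexes at 12 + 12: (C(12,6)/2^12)² = 0.05
- 8:16 or worse overall: 0.15
- 4:8 or worse in a given sex: 0.39; in at least one sex: 1 − (1 − 0.388)² = 0.63

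Averaged over all such allocations, bias is 0 and type I error is about 5%. Power at π = 0.5 is 0.71 without the term and 0.78 with it.

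**4. Which tests are exposed.** A visit shift that is the same at every time point cancels from time x trial. It does not cancel from the trial main effect, trial x sex, the paired t-tests at each time point, or sex comparisons within one trial. A period effect common to both sexes cannot move the sex main effect, because every completer contributes both visits.

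**5. Cost of adjusting when there is no period effect.** The standard error with the term is √(1/N + s̄²/Σ(s − s̄)²).

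- 12:12: √(1/24) = 0.204, power 0.80
- 8:16: s̄ = 1/3 in absolute value and Σ(s − s̄)² = 24 × (1 − 1/9) = 21.33, so √(0.0417 + 0.0052) = 0.217, noncentrality 0.6/0.217 = 2.77, power 0.75

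**The case against.** A reader might infer three stronger points, and the documents support none of them.

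- **That the protocol contradicts itself on order.** It calls the order balanced and names a random number generator. A generator can shuffle a balanced list, so the two statements are compatible. The text leaves open only how balance is reached and whether it holds within each sex. The probabilities in step 3 therefore describe an allocation that the protocol does not say it uses.
- **That period effects bias the RE-CON contrast.** Under the stated balance the contrast is unbiased and the test errs towards caution. Even with unblocked allocation, bias averages zero and overall type I error is about 5%. The 8.5% belongs to one realised split.
- **That all sex contrasts are affected.** The sex main effect is not.

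It is also fair to say that the protocol limits visit differences: at least a week between trials, the same menstrual phase, a 2-hour testing window, a fast, abstention from leg exercise, a hydration check and a replicated diet. The period effect may be small, and at 0.25 SD the loss is about one point of power. A statistical analysis plan that is not shown may add a term.

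What remains is that the protocol writes out a model for all variables, with named follow-up tests, and leaves out the factor it randomises. These controls may shrink a period effect, but they do not ensure that it is zero.

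**Conclusion.** The point holds as a modest weakness in the planned analysis: lost precision, and no protection if order turns out unequal. Under balance at N = 24, power falls from 0.80 to 0.79, 0.73 or 0.50 as the assumed period effect rises from 0.25 to 0.5 to 1.0 SD, with no bias. Imbalance could arise from an odd number in a sex (13 or 15 are allowed), dropout after the first trial, or unblocked allocation. A near-even split such as 8:7 matters little; a split such as 8:16 at 0.5 SD shifts the estimate by 0.17 SD. The exposed results are the trial main effect, trial x sex, the per-time-point paired tests and within-trial sex comparisons.

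All of these sizes rest on assumed period effects and on a 0.6 SD true difference, and they were computed for a paired comparison of one difference per person, not for the full repeated-measures model.

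**What to change.** - **Model.** Add order as a between-participant factor to the GLM, so that its trial x order term is the period effect; or fit period and sequence in a mixed model.
- **Follow-up tests.** Adjust the RE-CON comparison at each time point in the same way, by averaging the within-person differences over the two orders with equal weight instead of using a plain paired t-test.
- **Allocation.** State how order is balanced: permuted blocks within sex, preferably with an even number per sex, so that the balance also holds for trial x sex.

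The cost is an allocation list and one degree of freedom for order, or two if order x sex is kept as well. No visits or participants are added. Under balance with no period effect, power is essentially unchanged (0.80 either way). If order were as uneven as 8:16 and there were no period effect, the term would lower power from about 0.80 to 0.75; blocking avoids this.

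### The follow-up t-tests leave out each trial's PRE sample: the trial comparison loses precision, and a sex comparison run on concentrations can take a resting gap for a difference in response

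*Protocol*

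**What the plan says.** The protocol's Statistical Analysis section sets the main model: "General Linear Model (GLM) repeated measures analyses [time x trial x sex] will be used to compare trials (RE, CON) for all variables". Three kinds of follow-up come after a significant F ratio. Which F opens the gate (interaction or main effect) is not said.

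- Within each trial: "separate one-way repeated-measures ANOVA will be performed to assess the effect of time during each trial".
- Between trials: "separate paired-samples t-tests will be used to compare trials at each time point".
- Between sexes: "Separate independent t-tests will also be used to evaluate specific differences between sexes when applicable".

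Values are analysed as measured, or as natural logs if not normally distributed. No change score and no PRE covariate is named for either kind of t-test.

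Blood Collection, Handling and Storage shows that the baseline exists in both trials: "Blood samples during the experimental trials (PRE, IP, 15min, 30min, 60min"). Under Resistance Exercise Protocol, the two trials are run in balanced, randomized order at least a week apart. Research Design plans 12 to 15 men and 12 to 15 women.

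**The concern.** The sample-size paragraph frames the aim as a rise in I-FABP after exercise, which is a change from rest. The t-tests that will carry the statements about single time points and about sex compare levels, as far as the text goes.

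Two things are at stake. First, the trials are at least a week apart, so a participant's level can differ between the two days for reasons unrelated to exercise. That variation stays in the error of the paired t-test, although the PRE sample could remove part of it. Second, if men and women differ at rest, an independent t-test on post-exercise concentrations picks up that gap even when both respond equally. A log transformation does not help, since a proportional gap becomes a constant gap on the log scale.

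**Working it through.** **The plan's own figure.** The protocol gives no figure on this point. Its sample size (4 per group) rests on a percentage rise with no baseline mean, so it cannot be reproduced; nothing below uses it.

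**Step 1: does the main model share the fault?** Time x trial and time x trial x sex are contrasts of change over time, so anything constant within a participant's trial cancels. A numerical check on simulated data (24 participants, 2 trials, 5 times) added arbitrary participant-by-trial shifts. The time x trial F was 1.941 before and after. The trial main-effect F moved from 0.42 to 1.31. The interactions are safe, but main effects are not, and either could open the gate to the t-tests.

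**Step 2: precision of the trial comparison.** For each participant take the RE−CON difference at PRE and at a post-exercise time. Assume equal variances and correlation r. The documents give no r, so a range is shown. Relative to the plain paired t-test (variance 1):

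| r | change score, 2(1−r) | PRE-adjusted, 1−r² | equivalent sample size, 1/(1−r²) |
|---|---|---|---|
| 0.3 | 1.40 | 0.91 | 1.10 |
| 0.5 | 1.00 | 0.75 | 1.33 |
| 0.7 | 0.60 | 0.51 | 1.96 |

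Adjustment therefore cuts the variance by 9% to 49%. A plain change score is worse than doing nothing when r is below 0.5, so covariate adjustment is the better remedy. The factor 1−r² ignores the cost of estimating the slope. For one normally distributed covariate that cost is a factor 1+1/(n−3), which at n=24 is 1+1/21 = 1.05. The net factors are then about 0.91×1.05 = 0.96 at r=0.3 and 0.51×1.05 = 0.54 at r=0.7.

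**Step 3: is the trial comparison biased?** With no exercise effect, n=24 and r from 0.3 to 0.9, the plain paired t-test rejected in 4.8% to 5.0% of simulated trials, so its size holds. Only among trials where the mean PRE difference happened to exceed 1 SE did the rate rise, to about 12% (r=0.7) or 13% (r=0.8).

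**Step 4: sex comparison on levels.** Assume equal true response in both sexes, a resting gap of δ SD that persists after exercise, and a PRE-post correlation of 0.7. The t-test on levels has noncentrality δ√(n/2); for δ=0.5 and n=12 this is 0.5×√6 = 1.22. Simulated share of trials with p<0.05 at one time point:

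| resting gap | levels, 12 per sex | levels, 15 per sex | change from PRE |
|---|---|---|---|
| 0.3 SD | 11% | 12% | about 5% |
| 0.5 SD | 22% | 26% | about 5% |
| 0.8 SD | 47% | 56% | about 5% |

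A larger sample makes the error more frequent, because the gap is systematic. The levels columns do not depend on the correlation. They describe the t-test itself, without the preceding F test.

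**Step 5: would a simple mixed model do?** Not with a participant random effect alone. Four post-exercise draws from one trial day are correlated, and that model counts them as separate evidence. In null simulations (n=24; assumed day and response SDs 0.3 or 0.5, residual SD 0.5, between-person SD 1; 250 runs per setting) it rejected in about 30% of runs for the time-averaged RE−CON contrast, about the same for sex x trial, and about 9% for RE−CON at a single time, against a nominal 5%.

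**The case against.** The strongest reply is that the planned model already answers the question: its interactions remove day-level and resting differences, and the within-trial ANOVA includes that trial's PRE. This stands, and it confines the point to the follow-up t-tests and to any main effect that opens the gate to them.

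Three stronger readings are tempting, and the document does not support them.

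- A reader might infer that day-to-day differences will be mistaken for an exercise effect. Order is balanced and randomized, so they are noise, and PRE is itself one of the time points compared, so a chance imbalance would be visible.
- A reader might infer that the sex t-tests are fixed on concentrations. The protocol does not state their scale, so the bias is conditional.
- A reader might infer that one failed draw removes a participant from the whole analysis. A classical repeated-measures GLM does need every cell for a given marker, but the protocol states no missing-data rule, and one may stand in an analysis plan that is not shown. If 2% or 5% of ten draws were lost independently, 0.98^10 = 82% or 0.95^10 = 60% of participants would be complete. Those rates are assumptions, and losses through one cannula per trial would probably cluster, which removes fewer people. Each paired t-test needs only its own pair of values.

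It is also fair to say that r is unknown and that the gain at r=0.3 is small. For the lactulose/rhamnose ratio, PRE adjustment may add little, because the sugars are drunk at baseline.

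**Conclusion.** The point holds for the follow-up tests only. As written, the paired t-tests forgo a baseline that the trial collects. The loss is in precision: 9% to 49% of the variance for an assumed r of 0.3 to 0.7, slightly less after the cost of estimating the slope. They keep their type I error rate.

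The sex comparison is the more serious part, because sex is not randomized. If the independent t-tests are run on concentrations or their logs, an assumed resting gap of 0.5 SD is called a difference in about 22% of trials with 12 per sex and 26% with 15 per sex when the true response is equal. The size of any resting gap is not given in the protocol. Conclusions drawn from the time x trial and time x trial x sex interactions are unaffected.

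**What to change.** For I-FABP and endotoxin, on the log scale where needed, replace the post-exercise follow-up t-tests. At each post-exercise time, regress the participant's RE−CON difference on the RE−CON difference at PRE, sex and trial order. Code sex and order as ±½ and leave the PRE difference uncentred. The intercept is then the trial effect at equal PRE, and the sex coefficient is the sex x trial contrast. If independent t-tests between sexes are kept, state their scale and report them as comparisons of level, not of response.

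The alternative is a mixed model on all available draws. It needs a participant-by-trial random effect, or an unstructured covariance within each trial, in addition to the participant effect, and small-sample degrees of freedom. PRE can enter as a covariate or as a modelled time whose mean is set equal between trials; the second also keeps a participant without a PRE sample. Either form keeps participants who miss a post-exercise draw. A participant random effect alone must not be used.

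The cost is analysis wording and slightly more work. No extra samples are needed. PRE and order take two degrees of freedom beyond sex, which is already in the planned model; with 24 participants and four coefficients, 24−4 = 20 remain.
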